In the RELAX-AHF study 1161 patients were enrolled, 1138 of whom treated with serelaxin at 30 µg/kg/day or placebo (n=568 and 570 patients, respectively). The results showed a significant relief of dyspnea as measured by change from baseline on a 100-point visual analogue scale (VAS) over 5 days ($p=0.0075$), even though dyspnea reduction as measured using a 7-point, Likert scale over the first 24 hours (primary end-points) did not achieve statistical significance. The results also showed that, compared with conventional therapy, treatment with serelaxin improved signs and symptoms of patient congestion at Day 2 and significantly reduced WHF episodes through Day 5 and the overall length of index hospital stay, associated with a range of other in-hospital clinical benefits. WHF rates were significantly decreased by serelaxin in RELAX-AHF: significantly fewer patients in the serelaxin group experienced WHF event or death through Day 5 compared with the placebo group (6.5% vs. 12.0%, OR=0.51; 95% CI: 0.33, 0.77; RLX.CHF.003; data on file). Similar results were obtained for WHF through 14 days in placebo group 15.7% (KM) and serelaxin 11.4% (KM), $p=0.024$ ([Teerlink et al 2013](#)). Serelaxin provided sustained benefits beyond the initial 48 hours of infusion leading to a clinically and statistically significant 37% reduction in the risk of both cardiovascular and all-cause-mortality through Day 180. Serelaxin had favorable effects on the short-term changes in multiple laboratory markers of cardiac, renal, and hepatic damage known to be associated with long-term mortality in AHF. Serelaxin was well tolerated with no notable difference in the overall AE profile; a lower rate of AEs related to renal impairment in the serelaxin treatment arm compared with placebo was noted.

Based on these data, serelaxin represents a new treatment option in AHF, in addition to standard therapy, that may provide rapid and sustained dyspnea relief and improvement of other symptoms and signs of congestion. The findings obtained suggest serelaxin holds promise as the first evidence-based therapy for AHF to substantially improve patients' symptoms and clinical outcomes, including death.

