6.5 Safety

Safety will be assessed by comparing the serelaxin group to the standard of care only group with regard to the frequency of AEs/SAEs, changes in vital signs, physical examination findings, and clinical laboratory test results (chemistry, hematology, and urinalysis). All non-serious AEs will be collected through Day 5 and SAEs (regardless of causality) through Day 14. Any SAEs experienced after Day 14 should be reported to Novartis only if the investigator suspects a causal relationship to study treatment.

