2.2. TREATMENT GROUPS AND RANDOMIZATION

Subjects are randomized in a 2:1 ratio to receive one of the following:

- Serelaxin (30 µg/kg/day) as continuous 48-hour intravenous infusion plus standard of care.
- Standard of care only.

At baseline, all eligible patients who fulfill all inclusion/exclusion criteria are randomized via Interactive Response Technology (IRT) to one of the treatment arms.

	Statistical Analysis Plan
	Sponsor: NOVARTIS Protocol number: CRLX030A3301

The IRT assigns a randomization number to the patient, which links the patient to a treatment arm, and specifies a unique medication number (for patients randomized to serelaxin only) for the first package of investigational treatment to be dispensed to the patient. The randomization number is not communicated to the caller.

The randomization numbers are generated using the following procedure to ensure an unbiased treatment assignment. A patient randomization list is produced by the IRT provider using a validated system that automates the random assignment of patient numbers to randomization numbers. These randomization numbers are linked to the different treatment arms, which in turn are linked to medication numbers (for serelaxin arm only). A separate medication list is produced by or under the responsibility of Novartis Drug Supply Management using a validated system that automates the random assignment of medication numbers to packs containing the investigational drug.

Mis-randomized patients are those who have not been qualified for randomization, have been inadvertently randomized into the study and who did not take study drug. Mis-randomized patients are defined as cases where IRT calls were made by the site either prematurely or inappropriately prior to confirmation of the patient's final randomization eligibility and administration of serelaxin, when applicable, was not performed. These patients should have been considered screen failures as they did not meet eligibility criteria and should subsequently be discontinued from the study. Sites should notify IRT and contact their Novartis monitor as soon as possible if a patient is mis-randomized into the study.

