2.3. STUDY POPULATION

Similarly to the RELAX-AHF study, subjects are selected among patients who have been admitted with AHF, who have normal to elevated blood pressure (SBP \geq 125 mmHg at the start and at the end of the screening period) and have impaired renal function defined as an eGFR \geq 25 and \leq 75 ml/min/1.73m² at screening (calculated using the sMDRD equation).

The study plans to randomize approximately 3,183 patients in approximately 450 study sites mainly in Europe.

Inclusion criteria

Subjects must fulfill all of the following criteria at screening to be eligible for the study. The screening period is defined as the interval that begins at the time the informed consent is signed and ends with the qualification of the subject for entry into the study (i.e., when subject has met all eligibility criteria):

1. Able to provide written informed consent before any study-specific assessment is performed. The AHF diagnosis assessments performed as per current local institution/hospital standard practice or as part of routine clinical care can be used to support patient screening even if performed before obtaining informed consent.
2. Male or female \geq 18 years of age with body weight \geq 40 Kg and \leq 160 Kg.

	Statistical Analysis Plan
	
Sponsor: NOVARTIS
 
Protocol number: CRLX030A3301

3. Systolic blood pressure \geq 125 mmHg at the beginning of the screening period (after ICF signature) and at the end of the screening period (prior to randomization).
4. Admitted/hospitalized for AHF. AHF is defined as including all of the following measured at any time between presentation and the end of screening:
 - Persistent dyspnea at rest or with minimal exertion, at screening and at the time of randomization, despite standard background therapy for acute decompensated heart failure including intravenous furosemide of at least 40 mg total (or equivalent)
 - Pulmonary congestion assessed through physical examination and chest X-Ray obtained during routine clinical practice at any time between presentation and the end of screening (prior to randomization)
 - N-terminal pro B-type natriuretic peptide (NT-proBNP) \geq 2,000 pg/mL or BNP \geq 500 pg/mL. For patients treated with valsartan/sacubitril (Entresto[®]), BNP is not suitable and only NT-pro-BNP should be assessed.

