Treatment emergent AEs will be tabulated by System Organ Class (SOC) and Preferred Term (sorted in alphabetical order within each SOC) using the latest MedDRA dictionary, and by System Organ Class, Preferred Term and severity. Absolute and relative frequency of patients who have experienced each type of event will be presented; if the same patient reported more than one occurrence of the same AE with different intensity, the worst reported severity grade for each event for the patient will be used for the analysis. The most frequent treatment emergent AEs will also be tabulated by Preferred Term sorted by descending frequency for AEs with an incidence rate of at least 5% in the serelaxin group.

In addition, treatment emergent adverse events associated with

- worsening heart failure (WHF)/all cause death through Day 5
- confirmed systolic blood pressure decrease event (CBPDE)

will be summarized by system organ class and preferred term. These AEs are determined by taking the answer “Yes” to the questions “Does AE meet the definition of Endpoint?” and “Does AE meet the definition of Systolic Blood Pressure Decrease Event?”, respectively.

Treatment emergent SAEs will be summarized similarly. Treatment emergent SAEs will be summarized by time period of onset, i.e., through Day 5 and through Day 14. Treatment emergent SAEs are defined as those which start after treatment start for serelaxin group, or after randomization for Standard of Care group.

All study-drug-related AEs, AEs with an outcome of death, AEs leading to permanent discontinuation of treatment will be listed with all their details. Time from the treatment start for serelaxin group or from randomization for Standard of Care group, to the AE start/end date, will be also computed. Elapsed days, hours and minutes plus 1 minute will be reported on the listing.

In case of an ongoing event, no days relative to the end of the event will be computed.

In case of missing time of start or end of an event, no relative days will be computed.

Safety risks and events of interest

Adverse events will be also presented according to the search strategies using the latest MedDRA dictionary version available before database lock, as specified in the Case Retrieval Strategy (CRS) defined by Novartis. Adverse events will be characterized as safety risks and as events of interest according to the rules specified in Table 5.3-1 and Table 5.3-2, respectively.

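### The table of most frequent adverse events selects terms on the serelaxin rate alone, so terms below 5% on serelaxin but at or above 5% on standard of care are left out

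*SAP*

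**What the plan says.** SAP 5.3 (Adverse events) first requires all treatment-emergent adverse events to be tabulated by System Organ Class and Preferred Term, and again by severity, with no frequency cut-off. It then adds a table of the most frequent events by Preferred Term, "sorted by descending frequency for AEs with an incidence rate of at least 5% in the serelaxin group". The SAP gives no SOC, either-group or overall criterion for this table.

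Protocol 6.5 states the purpose that the safety tables serve: "Safety will be assessed by comparing the serelaxin group to the standard of care only group with regard to the frequency of AEs/SAEs".

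Protocol 9.5.2 asks for summaries by System Organ Class and Preferred Term and by severity. It sets no 5% rule, so the one-arm filter comes from the SAP alone.

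**The concern.** A comparative table should choose its rows by a rule that treats the arms alike. Here a term enters on the observed result of one arm, with two effects.

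- **Omission.** A term below 5% on serelaxin and at or above 5% on SOC is not listed. A term with those rates exchanged is listed.
- **Selection.** A term near the cut-off is listed only when its serelaxin count happens to be high enough. Its serelaxin rate, given that it is listed, is biased upwards. The SOC rate beside it is not selected and stays unbiased.

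What is at stake is how evenly this one table shows common events. The question is not idle, because the sponsor has reason to expect some events to be less frequent on serelaxin. For the earlier phase III trial, Protocol 1.1 says that "a lower rate of AEs related to renal impairment in the serelaxin treatment arm compared with placebo was noted". Protocol section 7 also requires every worsening heart failure (WHF) endpoint to be recorded as an adverse event. A reader who uses only the 5% table would not see a term that serelaxin brings below 5%.

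**Working it through.** The 5% cut-off is a chosen threshold, so the plan has no figure of its own to reproduce. The check sizes the two effects.

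**Inputs.** SAP 2.2 gives 2:1 allocation ("Subjects are randomized in a 2:1 ratio to receive one of the following") and SAP 2.3 gives approximately 3,183 patients. Hence serelaxin n = 3,183 × 2/3 = 2,122 and SOC n = 1,061. The Safety set is assumed equal to these numbers. The true event rates are assumptions, shown over a range.

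**Cut-offs.** Serelaxin: 0.05 × 2,122 = 106.1, so at least 107 patients. SOC: 0.05 × 1,061 = 53.05, so at least 54 patients.

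**Omission.** Let a = P(X ≥ 107) with X binomial (2,122, serelaxin rate), and b = P(Y ≥ 54) with Y binomial (1,061, SOC rate). Then:

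- listed under the SAP rule: a
- listed under an either-group rule: 1 − (1 − a)(1 − b)
- omitted by the SAP rule although SOC reaches 5%: (1 − a) × b

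| True rate, serelaxin / SOC | SAP rule | Either-group rule | Omitted although SOC ≥ 5% |
|---|---|---|---|
| 4% / 6% | 0.010 | 0.909 | 0.899 |
| 4% / 7% | 0.010 | 0.995 | 0.985 |
| 4.5% / 6% | 0.125 | 0.920 | 0.794 |
| 5% / 8% | 0.478 | 1.000 | 0.522 |
| 5% / 5% | 0.478 | 0.722 | 0.243 |
| 6.5% / 12% | 0.998 | 1.000 | 0.002 |
| 6% / 4% | 0.974 | 0.975 | 0.001 |
| 7% / 4% | 1.000 | 1.000 | 0.000 |

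For example, at 4.5% / 6%, a = 0.125 and b = 0.908, so the either-group probability is 1 − 0.875 × 0.092 = 0.920. The asymmetry is clearest between 4% / 7% (listed with probability 0.010) and 7% / 4% (listed with probability 1.000).

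An omitted term need not be a trivial one. At 4% / 7% the pooled standard error is √[0.05 × 0.95 × (1/2,122 + 1/1,061)] = 0.0082. The unpooled one is √(0.04 × 0.96/2,122 + 0.07 × 0.93/1,061) = 0.0089. Power at two-sided 0.05 is Φ[(0.03 − 1.96 × 0.0082)/0.0089], about 94%.

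**Selection.** With the same true rate p in both arms, the mean serelaxin rate among listed terms under the SAP rule is E[X/2,122 | X ≥ 107], while the SOC mean stays at p. Under the either-group rule both means are conditional on X ≥ 107 or Y ≥ 54. Rates are in percent. The differences are serelaxin minus SOC, in percentage points, computed before rounding.

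| True rate, both arms | SAP rule: P(listed) | Serelaxin / SOC | Difference | Either group: P(listed) | Serelaxin / SOC | Difference |
|---|---|---|---|---|---|---|
| 4.0 | 0.010 | 5.18 / 4.00 | +1.18 | 0.055 | 4.21 / 5.07 | −0.87 |
| 4.5 | 0.125 | 5.25 / 4.50 | +0.75 | 0.296 | 4.76 / 5.03 | −0.27 |
| 5.0 | 0.478 | 5.39 / 5.00 | +0.39 | 0.722 | 5.14 / 5.19 | −0.05 |
| 5.5 | 0.834 | 5.65 / 5.50 | +0.15 | 0.957 | 5.53 / 5.54 | −0.01 |
| 6.0 | 0.974 | 6.03 / 6.00 | +0.03 | 0.998 | 6.00 / 6.00 | 0.00 |

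The inflation disappears as the true rate rises above the cut-off. Well below it, the inflation per listed term is larger, but such terms are seldom listed.

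**The case against.** The case against making much of this is strong.

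- **Nothing is lost from the report.** The SAP presents the 5% table as an addition to a complete table that keeps every term. No test or decision depends on it. This stands.
- **The two motivating examples are covered elsewhere without a cut-off.** SAP 5.3 summarizes adverse events associated with WHF or death separately. It also tabulates cardiac failure and renal impairment as events of interest, by treatment group and down to Preferred Term. WHF is also part of the primary endpoint, and renal deterioration is a compared secondary endpoint in SAP 5.2. This stands.
- **A profile of common events on the new drug is a legitimate description.** That is true, and Protocol 9.5.2 is not contradicted. It does not explain why a table meant to support a two-arm comparison should choose its rows from one arm.
- **An either-group rule has a selection effect of its own.** Because the SOC arm is half the size, its observed rates are noisier and selection then favours serelaxin slightly. This stands and counts as a cost of the change.

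A reader might also infer that the table cannot show events that serelaxin reduces. The rule does not support that: any term observed at 5% or more on serelaxin is listed, however high the SOC rate. At the earlier trial's rates for WHF or death in Protocol 1.1, 6.5% against 12.0%, a term would be listed with probability 0.998. Nor can the rule be read as concealing harm from serelaxin, since no serelaxin rate observed at 5% or more can be left out.

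**Conclusion.** The point holds as a minor asymmetry in one supplementary table. The terms affected are those observed below 5% on serelaxin and at or above 5% on SOC, and for true rates such as 4% and 7% the omission is close to certain. The upward selection of serelaxin rates is below half a point for true rates of 5% or more. Both effects make serelaxin look slightly worse, not better.

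The sizes rest on a Safety set equal to the planned enrolment split exactly 2:1, and on assumed true event rates. That the rule looks at one arm only is plain from the text and needs no assumption. This is a cheap improvement to the reporting and does not threaten the trial's safety conclusions.

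**What to change.** In SAP 5.3, change the entry condition for the most-frequent table from 5% in the serelaxin group to 5% in either treatment group, and state that both arms are shown for every listed term. A between-arm risk difference with a 95% confidence interval per term would be a useful option, but the correction does not depend on it.

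The cost is one phrase and a slightly longer table. The change makes entry symmetric, but it does not remove selection. For terms with equal true rates it leaves an effect in favour of serelaxin of about 0.05 points at 5% and 0.27 points at 4.5%, against 0.39 and 0.75 points in the other direction now. At 4% the reversed effect is 0.87 points, and such a term is listed with probability 0.055 instead of 0.010. A footnote to the table should say that rates close to 5% are affected by the entry rule and that the complete table is the reference.

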6.5.5 Electrocardiogram (ECG)

ECGs will be performed and interpreted locally at screening and at Day 5 and at discharge. The ECG interpretation and the person interpreting the ECG must be recorded in the source documents.

ECGs must be recorded after 10 minutes rest in the supine position to ensure a stable baseline. The preferred sequence of cardiovascular data collection during study visits is ECG collection first, followed by vital signs, and blood sampling. The Fridericia QT correction formula (QTcF) should be used for clinical decisions.

Single 12 lead ECGs are collected. The original ECGs on non-heat-sensitive paper or a certified copy on non-heat sensitive paper, appropriately signed, should be collected and archived at the study site.

Each ECG tracing should be labeled with study number, subject initials, subject number, date and time, and filed in the study site source documents. For any ECGs with subject safety concerns, two additional ECGs should be performed to confirm the safety finding. Clinically significant ECG findings prior to dosing with investigational treatment must be discussed with the sponsor.

Clinically significant abnormalities should be recorded on the relevant section of the medical history/Current medical conditions/AE eCRF page as appropriate.

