Hy's chemistry category	ALT or AST >3x ULN and TBL >1.5x ULN	
	ALT or AST >3x ULN and TBL >2x ULN	
	ALT or AST >5x ULN and TBL >2x ULN	
	ALT or AST >8x ULN and TBL >2x ULN	
TBL & ALP	ALT or AST >10x ULN and TBL >2x ULN	
	ALT or AST >3x ULN and TBL >2x ULN and ALP <2x ULN	Subjects with a post BL value
	TBL >1.5x ULN and ALP >2x ULN	
	TBL >2x ULN and ALP >2x ULN	
Isolated TBL	TBL >1.5x ULN & ALT and AST ≤3x ULN and ALP≤2x ULN	
	TBL >2x ULN & ALT and AST ≤3x ULN and ALP ≤2x ULN	
	TBL >3x ULN & ALT and AST ≤3x ULN and ALP ≤2x ULN	
Isolated ALP	ALP >2x ULN & ALT and AST ≤3x ULN and TBL ≤1.5x ULN	
	ALP >3x ULN & ALT and AST ≤3x ULN and TBL ≤1.5x ULN	
	ALP >5x ULN & ALT and AST ≤3x ULN and TBL ≤1.5x ULN	

Plots showing the relationship between maximum TBL and ALT or AST at any visit (eDISH plot for the evaluation of drug-induced serious hepatotoxicity) will also be provided.

Laboratory data: urinalysis

Summary statistics for data about urinalysis will be provided at each assessment time point by treatment group. For each parameter result, absolute and relative frequencies of patients reporting it will be provided. Percentages will be computed considering patients with non-missing information at each assessment time point.

Electrocardiogram (ECG)

The number and proportion of patients by procedure performed and overall interpretation will be provided at each assessment time point by treatment group. Percentages will be computed considering patients with non-missing information at each assessment time point. Summary statistics will be provided at each assessment time point by treatment group.

Heart rate (beats/min), mean PR duration (msec), mean QT duration (msec), corrected QT Fridericia interval (QTcF) and mean QRS duration (msec) will be described, providing number of observations, mean, standard deviation, median, first and third quartiles, minimum and maximum at each assessment time point by treatment group.

The number and proportion of patients with the following criteria at any post-baseline visit will be presented:

	Statistical Analysis Plan
	Sponsor: NOVARTIS
	Protocol number: CRLX030A3301

Table 5.3-6: Criteria for ECG categorical analysis

Topic	Parameter categories	Criterion for denominator
QT/QTcF	QT/QTcF >450 msec	Subjects with QT/QTcF ≤450 msec at BL
	QT/QTcF >480 msec	Subjects with QT/QTcF ≤480 msec at BL
	QT/QTcF >500 msec	Subjects with QT/QTcF ≤500 msec at BL
	QT/QTcF >450 msec; males only	Male subjects with QT/QTcF ≤450 msec at BL

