	QT/QTcF >460 msec; females only	Female subjects with QT/QTcF ≤460 msec at BL
	QT/QTcF increase from BL >30 msec	Subjects with a non-missing value at BL and post BL
	QT/QTcF increase from BL >60 msec	Subjects with a non-missing value at BL and post BL
PR	PR >200 msec	Subjects with PR ≤200 msec at BL
	PR >220 msec	Subjects with PR ≤220 msec at BL
	PR > 200 msec and change from BL ≥25%	Subjects with PR ≤200 msec at BL
QRS	QRS >110 msec and change from BL ≥25%	Subjects with QRS ≤110 msec at BL
	QRS >120 msec and change from BL ≥25%	Subjects with QRS ≤120 msec at BL
Heart Rate	Heart rate >100 bpm and change from BL ≥25%	Subjects with heart rate ≤100 bpm at BL
	Heart rate <50 bpm and change from BL ≥25%	Subjects with heart rate ≥50 bpm at BL

In addition, shift tables comparing baseline ECG overall interpretation (normal, clinically insignificant abnormality, clinically significant abnormality) with Day 5/discharge ECG overall interpretation (normal, clinically insignificant abnormality, clinically significant abnormality) will be provided by treatment group.

A listing of clinically significant abnormalities in ECG evaluations will be provided.

Echocardiography

Echocardiography is not considered as study related procedures and is performed according to local diagnostic practice.

Overall interpretation will be described by providing the number and proportion of subjects in each category at each assessment time point by treatment group. Percentages will be computed considering patients with non-missing information at each assessment time point.

LV Ejection Fraction (%) will be described by means of summary statistics (i.e., number of observations, mean, standard deviation, median, first and third quartiles, minimum and maximum) at each assessment time point by treatment group.

Systolic blood pressure decrease event

	Statistical Analysis Plan
	Sponsor: NOVARTIS Protocol number: CRLX030A3301

A confirmed systolic blood pressure decrease event (CBPDE) is defined as systolic blood pressure decreases by > 40 mmHg from just before the study drug infusion at baseline but is ≥ 100 mmHg in 2 consecutive measurements 15 minutes apart, or if in 2 consecutive measurements 15 minutes apart, systolic blood pressure reduces to < 100 mmHg, as reported in the "Systolic blood pressure decrease event – vital signs" eCRF.

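### SAP Table 5.3-6 applies its QT cut-offs to uncorrected QT as well as QTcF, so a slower heart rate alone can meet the increase criteria; its threshold rows also do not require a post-baseline ECG

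*SAP*

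**What the plan says.** The ECG part of SAP 5.3 treats uncorrected QT and QTcF as two variables in its continuous summaries: "mean QT duration (msec), corrected QT Fridericia interval (QTcF"). Table 5.3-6 then joins them. Its five absolute rows (above 450, 480 and 500 msec for everyone, above 450 for men, above 460 for women) and its two increase rows ("QT/QTcF increase from BL >30 msec" and "QT/QTcF increase from BL >60 msec") all refer to QT/QTcF. The SAP does not say whether the slash means each variable in its own row or either one in a common row. A patient counts on the strength of a single later ECG: "The number and proportion of patients with the following criteria at any post-baseline visit will be presented".

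The denominators follow two rules. The absolute rows use baseline status alone, for example "Subjects with QT/QTcF ≤450 msec at BL". The increase rows use "Subjects with a non-missing value at BL and post BL". The PR, QRS and heart-rate rows have the baseline-only form.

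Protocol 6.5.5 sets the timing, "ECGs will be performed and interpreted locally at screening and at Day 5 and at discharge", and names the correction: "The Fridericia QT correction formula (QTcF) should be used for clinical decisions".

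**The concern.** The baseline ECG is recorded at screening, during acute heart failure. Exclusion criterion 3 (Protocol 4.2) removes only patients with a persistent rate above 130 bpm. The comparison ECGs come at Day 5 and discharge. If the rate has slowed by then, uncorrected QT is longer even when repolarization has not changed, so an increase row applied to uncorrected QT partly records heart-rate recovery. If the slash means either variable, such patients also enter the only count shown.

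The denominators raise a second, independent question. A patient who dies or is lost before the first post-baseline ECG cannot meet any criterion, yet stays in the denominator of every row that looks only at baseline. Membership of the Safety set does not prevent this, because SAP section 3 accepts a statement of no adverse events as the post-baseline assessment.

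**Working it through.** **Inputs.** The cut-offs are those of Table 5.3-6; the ECG times and the Fridericia correction are from Protocol 6.5.5. The documents state no QT result to reproduce and give no heart-rate (HR) or QTcF values, so the values of both used below are assumptions.

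**1. Increase rows.** Fridericia: QTcF = QT / (60/HR)^(1/3), so QT = QTcF × (60/HR)^(1/3). Hold QTcF at 420 msec and change only the rate:

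| HR, screening to later | QT, msec | Change | >30 met | >60 met |
|---|---|---|---|---|
| 90 to 70 | 367 to 399 | +32 | yes | no |
| 100 to 75 | 354 to 390 | +36 | yes | no |
| 100 to 60 | 354 to 420 | +66 | yes | yes |
| 100 to 80 | 354 to 382 | +27 | no | no |
| 90 to 75 | 367 to 390 | +23 | no | no |
| 80 to 70 | 382 to 399 | +17 | no | no |

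The QTcF change is 0 in every line. The choice of QTcF matters little: 100 to 75 bpm gives +34 at 400 msec and +37 at 440 msec.

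The later rate below which an increase of d msec is exceeded is 60 / [(60/HR0)^(1/3) + d/QTcF]^3, where HR0 is the screening rate. At QTcF 420:
- d = 30: 71.1 bpm from 90, 78.4 from 100, 85.5 from 110, which are falls of about 19, 22 and 25 bpm.
- d = 60: 57.1 bpm from 90, 62.5 from 100, 67.8 from 110.

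The effect is therefore mainly in the >30 msec row.

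**2. Absolute rows.** At 60 bpm QT equals QTcF; above 60 bpm QT is the smaller. With QTcF constant, QT exceeds 450 only if HR is below 60 × (QTcF/450)^3. That is 48.8 bpm at QTcF 420, 60.0 at 450 and 72.8 at 480. Two errors follow:
- *Under-counting.* QTcF 500 at 85 bpm gives QT = 500 × (60/85)^(1/3) = 445, so the uncorrected >450 row misses it.
- *Mislabelling as new.* With QTcF constant at 470, 90 to 60 bpm moves QT from 411 to 470. The patient enters the denominator of those at or below 450 and is then counted as a new case, although QTcF was above 450 throughout. The change is +59 msec, which meets the >30 row but not the >60 row.

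**3. Denominators.** Let p be the proportion meeting a criterion among at-risk patients with a post-baseline ECG, and m the share of at-risk patients without one. The increase-row rule reports p. The threshold-row rule, followed literally, reports p × (1 − m). For an assumed m of 5% to 10%, that is 0.95p to 0.90p, a relative understatement equal to m. Elsewhere SAP 5.3 asks for post-baseline data explicitly: the relative-change laboratory criteria need evaluable values at both visits, and Table 5.3-5 counts patients with a post-baseline value.

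**The case against.** The slash may simply mean that each criterion is applied to each variable with its own denominator. The QTcF rows then already exist, are untouched by heart rate, and the change only removes supplementary rows. This stands as far as it goes, but the SAP does not state it, and the uncorrected rows would still carry cut-offs that rate alone can meet.

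On denominators, it can be said that the table is silent rather than wrong. The same ECG subsection bases percentages on non-missing data by time point, and ECGs are planned at two later occasions. However, that sentence follows the summary of overall interpretation, not this any-visit table, and the two increase rows show that the post-baseline condition was written in where it was wanted.

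A reader might also infer more than the documents support:
- *That the table will hold many false cases.* Without heart-rate data this cannot be said. Modest falls do not trigger the >30 row, and a patient with QTcF at or below 450 and a rate of at least 60 bpm cannot cross an absolute cut-off through rate alone.
- *That the QT prolongation event of interest is distorted.* That event (Table 5.3-2) is a MedDRA search of reported adverse events. Table 5.3-6 does not feed it.
- *That the comparison of arms is biased.* This needs a heart-rate change that differs by arm, for which the documents offer no evidence. Heart rate is also summarized by arm at each ECG time point, so such a difference would be visible.
- *That the SAP contradicts the protocol.* The protocol's sentence on QTcF concerns clinical decisions, not descriptive tables.

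**Conclusion.** The point holds in a limited form and is minor. Applied to uncorrected QT, the increase rows, chiefly >30 msec, can be met by slowing of about 19 to 25 bpm from 90 to 110 bpm with QTcF unchanged at an assumed 420 msec. The absolute rows mostly err the other way, by under-counting above 60 bpm, and can date a long-standing long QTcF as new. How often either happens is unknown. Separately, the baseline-only denominators understate the percentages by the share without a post-baseline ECG, if they are programmed as written; the 5-10% used for that share is an assumption. The table is descriptive, and the primary analysis is not affected.

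**What to change.** In Table 5.3-6, write QTcF in place of QT/QTcF in all seven criteria and in their denominators. Keep uncorrected QT in the continuous summaries, where it already stands. Add a non-missing post-baseline value of the relevant parameter to every denominator, including the PR, QRS and heart-rate rows, in line with the two increase rows.

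The cost is SAP wording and programming of one descriptive table, with fewer outputs and no new data. The small loss is the categorical tabulation of uncorrected QT. If the sponsor wants to keep it, separate rows marked as not rate-corrected would remove the ambiguity.
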